### 4.2.3 Rationale for Endpoints

#### 4.2.3.1 Safety Endpoints

Clinically, the addition of Pembrolizumab to Cisplatin and radiation has yet to be explored. Pre-clinically, the addition did not add any unexpected toxicity in small analyses. Based on the current safety profile of Pembrolizumab alone, and the fact that the toxicities are unique to immunotherapy compared to radiation and chemotherapy, we do not expect to observe any additional adverse effects and that this will therefore be a safe combination. However, because this combination has not yet been explored in this setting (although many clinical trials are currently being designed), we will continue to monitor safety throughout this study using CTCAE guidelines. We will perform a lead-in of 8 patients in each arm in order to determine any unexpected toxicities beyond what had been documented for these therapies. As long as current standard of therapy is not felt to be significantly impacted (delay in >2 out of 8 patients in each arm), the trial will proceed.

[figure not shown]

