#### **5.2.2.2 Pembrolizumab Guidelines**

Pembrolizumab 200 mg will be administered as a 30 minute IV infusion every 3 weeks. Infuse pembrolizumab (MK-3475) over approximately 30 minutes, with a window of -5 and +10 minutes, through a peripheral line or indwelling catheter. The first dose will be given no more than 3 weeks and no less than 7 days prior to resection. Ideally, the pre-surgery dose of Pembrolizumab will be given between 1-2 weeks before surgery. Post-surgery, Pembrolizumab will be between 4 and 11 weeks and will continue during radiation and 3 months after completion. The first adjuvant Pembrolizumab dose is to begin 1 week prior to radiation.

Pembrolizumab will be administered before Cisplatin on days they are given together. If fluids are administered along with Pembrolizumab, then hydration should include only NS. Radiation may be given before or after infusions. If a Pembrolizumab dose is missed outside the +/-1 day window up to week 7 and +/-3 day window week 10 and beyond per the schedule of events, it should be skipped and not made up.

The Pharmacy Manual contains specific instructions for the preparation of the Pembrolizumab infusion fluid and administration of infusion solution.

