### **5.2.2.3 Lead-in Population for Safety Analysis**

The first eight patients from each arm will be enrolled as the lead-in population. Safety analysis will be performed with this population and will be analyzed on a rolling basis. Weekly conference calls with all the sites will be held to determine if any of these first 8 patients have experienced a dose limiting toxicity, DLT, (described below) to evaluate the safety of the combination as well as the safety of administering Pembrolizumab before surgery. Safety analysis will be considered complete for each arm at four weeks after the eighth patient has finished CRT. Patients will continue to be enrolled past the initial safety cohort, but if at any time, safety analysis reveals >2 out of the 8 patients in the safety cohort have developed a DLT, then no further patient may be enrolled to that arm due to excess toxicity with this combination. If the safety event occurs prior to surgery only, than the pre-surgery dose of Pembrolizumab will be discontinued for the following patients but the trial will continue with adjuvant treatment only.

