#### **5.2.2.3.1 Dose Limiting Toxicity**

Dose limiting toxicity will be defined as any adverse effect, that in the treating investigator’s opinion, was felt to be due to Pembrolizumab and significantly delayed standard of care treatment (> 7 days delay in surgery, >3 days for radiation, and/or >7 days for Cisplatin dose). In these patients, Pembrolizumab will be discontinued permanently.

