Nausea and Vomiting: Maximum supportive therapy will be given, and Cisplatin will be continued at full dose for  $\leq$  grade 2 nausea and vomiting. For grade 3 nausea and vomiting refractory to supportive therapy, Cisplatin will be held until recovery to < grade 2. No dose reductions will be made.

Mucositis: Significant mucositis (grade 3-4, CTCAE, v. 4) is expected from radiation and Cisplatin and should not be a reason for a treatment break, unless it significantly interferes with fluid intake or nutrition. Aggressive supportive care is encouraged as well as consideration of a PEG tube if not already

done.

Ototoxicity: For clinical hearing loss not requiring a hearing aid, reduce Cisplatin by 2 dose levels (23mg/m^2). For hearing loss requiring a hearing aid, discontinue Cisplatin. For grade 2-3 tinnitus (CTCAE, v. 4) at the time of retreatment, hold Cisplatin until improvement to grade 1 or less and then reduce the following doses of Cisplatin by 2 dose levels. If tinnitus does not improve to grade 1 or less by the last day of radiation therapy, discontinue Cisplatin. An audiogram is recommended when there is any report of significant change in hearing and/or an increase in tinnitus.

Other Toxicities: For any other grade 3-4 adverse events, hold Cisplatin until toxicities have recovered to grade 1 or less. Dose may be reduced by 1 or 2 dose levels for next treatment if felt necessary by discretion of investigator.

If any doses of Cisplatin are skipped due to hematologic, neurologic, renal, or other adverse events, these doses will NOT be made up at end of treatment. Cisplatin will continue only during time of radiation treatment. If a weight change of  $\geq 10\%$  occurs, the following Cisplatin doses should be adjusted.

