#### Cisplatin

Cisplatin will be given at 40mg/m^2 starting concurrently with radiation one week after first post-surgery Pembrolizumab dose is given. Cisplatin will be given weekly for 6 doses during the radiation treatment. Any skipped doses will not be made up at the completion of radiation therapy.

**Formulation:** Each vial contains 10 mg of DDP, 19 mg of sodium chloride, 100 mg of mannitol, and hydrochloric acid for pH adjustment. One vial is reconstituted with 10 ml of sterile water. The pH range will be 3.5 to 4.5. Cisplatin injection also is available from the manufacturer in aqueous solution, each ml containing 1 mg Cisplatin and 9 mg NaCl and HCl or NaOH to adjust pH.

**Mechanism of Action:** The dominant mode of action of Cisplatin is inhibition of the incorporation of DNA precursors, although protein and RNA synthesis are also inhibited. Although Cisplatin is thought to act as an alkylating agent, there are data to indicate that its mode and sites of action are different from those of nitrogen mustard and other standard alkylating agents.

**Administration:** Cisplatin will be given as a bolus, infused over 1-2 hours along with appropriate hydration and anti-emetics.

**Storage and Stability:** Reconstituted solution of Cisplatin is stable for 20 hours when stored at 27°C and should be protected from light if not used within 6 hours. The vials and injection should not be refrigerated. Cisplatin has been shown to react with aluminum needles, producing a black precipitate within 30 minutes.

**Adverse Events:** Human toxicity includes nausea, vomiting, renal toxicity (with an elevation of BUN and creatinine and impairment of endogenous creatinine clearance, as well as renal tubular damage, which appears to be transient), ototoxicity (with hearing loss that initially is in the high-frequency range, as well as tinnitus), and hyperuricemia. Much more severe and prolonged toxicity has been observed in patients with abnormal or obstructed urinary excretory tracts. Myelosuppression, often with delayed erythrosuppression, is expected as well.

**Supply:** Cisplatin is commercially available. The use of drug(s) or combination of drugs in this protocol meet the criteria described under Title 21 CFR 312.2(b) for IND exemption.

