### **5.8 Subject Replacement Strategy**

Patients who are unfit or unwilling to continue study after resection will be replaced. Patients who choose not to undergo surgical resection after initial dose of Pembrolizumab will be replaced. In addition, any patient who does not complete at least 1 week of adjuvant treatment will also be replaced.

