## 8.2 Statistical Analysis Plan

### 8.2.1 Safety Endpoints

The safety endpoints are all adverse events graded from 1 to 5 described in Section 7.

The Lead-in population will be assessed for DLTs as described in section 5.2.2.3.1.

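### The lead-in stopping rule cannot count a pembrolizumab-attributed death that arises after the patient's own chemoradiation, because a DLT requires a delay of standard treatment

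*Combined protocol and SAP*

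**What the plan says.** Section 5.2.2.3.1 sets two conditions joined by *and*. The treating investigator must attribute the event to pembrolizumab, and the event must have "significantly delayed standard of care treatment (> 7 days delay in surgery, >3 days for radiation, and/or >7 days for Cisplatin dose". Neither toxicity grade nor death appears in the definition.

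Section 4.2.3.1 gives the same logic as the rationale: the trial goes on unless standard therapy is materially affected, expressed as "delay in >2 out of 8 patients in each arm".

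Section 5.2.2.3 applies the definition to the first eight patients in each arm. Weekly calls with all sites look for DLTs while enrolment continues, and more than 2 DLTs among the 8 closes the arm. On the length of the window it says: "Safety analysis will be considered complete for each arm at four weeks after the eighth patient has finished CRT".

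Section 8.2.1 adds no second definition: "The Lead-in population will be assessed for DLTs as described in section 5.2.2.3.1".

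On exposure, section 5.2.2.2 (Pembrolizumab Guidelines) says that pembrolizumab "will continue during radiation and 3 months after completion".

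On replacement, section 5.8 says that "any patient who does not complete at least 1 week of adjuvant treatment will also be replaced". It does not say whether a replaced lead-in patient stays in the DLT tally.

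**The concern.** The observation window and the definition do not fit together. The window deliberately runs past the end of CRT, and pembrolizumab is still being given then. Yet the only events that count are those that held up surgery, radiation or cisplatin, and none of these remains once the patient's own CRT is over. The most serious outcome that a safety lead-in exists to detect, a death attributed to the study drug, then falls outside the count.

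This matters because more than 2 of 8 is the only numerical stopping rule in the plan. Section 5.9 is qualitative. The exact tests in sections 8.1.1 and 8.2.4.1, against 50% and 39%, carry no stopping action. The interim analysis in section 8.2.4.2 is discretionary and has no threshold. Patients keep entering an arm during its lead-in, so they depend on this rule.

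**Working it through.** The plan states no operating characteristic for the lead-in rule (no target DLT rate, no stopping probability), so there is no figure to reproduce. The check is a reading of the text, followed by a small calculation of what the fix costs.

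**1. Is pembrolizumab given after CRT but inside the window?** Inputs: Table 2 (section 5.2) gives 7 doses including the presurgical one, every 3 weeks, with adjuvant dosing starting 7 days before CRT. Section 5.2.2.3.1 of the radiation guidelines (Dose Specifications) gives 30 to 33 fractions, once daily; Table 2 sets Monday to Friday.

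- Adjuvant pembrolizumab: 7 − 1 = 6 doses, in weeks 1, 4, 7, 10, 13 and 16, counting from the first adjuvant dose.
- Radiation: weeks 2 to 7 with 30 fractions, or into week 8 with 33.
- Four weeks after radiation: week 11 or week 12.

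Three of the six adjuvant doses (weeks 10, 13, 16) come after radiation. The week 10 dose lies inside the four-week period even for the eighth patient. For patients 1 to 7 the window lasts until four weeks after the *eighth* patient finishes, so later doses can fall inside it too, depending on accrual.

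**2. Can an event arising in that period be a DLT?**

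| Condition in 5.2.2.3.1 | Status after the patient's own CRT |
|---|---|
| Attributed to pembrolizumab | Possible |
| Surgery delayed >7 days | Impossible, surgery done |
| Radiation delayed >3 days | Impossible, radiation done |
| Cisplatin delayed >7 days | Impossible, cisplatin is given only during radiation |

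The delay condition is mandatory and cannot be met. An event that had already caused a qualifying delay does count, but through the delay and not through a later death.

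**3. What does the tally show?** The rule triggers at 3 or more of 8. The deaths below are attributed, arise after CRT and occur in patients without an earlier qualifying delay.

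| Delay DLTs | Attributed deaths after CRT | Tally as written | Triggers? | Tally if such deaths count | Triggers? |
|---|---|---|---|---|---|
| 2 | 1 | 2 | No | 3 | Yes |
| 0 | 3 | 0 | No | 3 | Yes |

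**4. What does counting such deaths cost?** With per-patient DLT probability *p*,

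P(X ≥ 3) = 1 − (1−p)^8 − 8p(1−p)^7 − 28p²(1−p)^6.

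- p = 0.10: 1 − 0.4305 − 0.3826 − 0.1488 = 0.038
- p = 0.11: 1 − 0.3937 − 0.3892 − 0.1684 = 0.049

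The same formula over a range of assumed base rates, with 1 or 5 percentage points added for newly counted events:

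| Assumed base rate | As written | +1 point | +5 points |
|---|---|---|---|
| 5% | 0.006 | 0.010 | 0.038 |
| 10% | 0.038 | 0.049 | 0.105 |
| 20% | 0.203 | 0.225 | 0.321 |

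All of these rates are assumptions.

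**The case against.** The delay endpoint is a choice. The safety hypothesis in section 3.1 and the rationale in section 4.2.3.1 both ask whether pembrolizumab interferes with standard therapy, and a rule built on delay answers that question. An attributed death would also not pass unseen. Section 7.2.3.1 requires deaths not due to progression to reach the sponsor within 24 hours, up to 90 days after treatment ends or until new anticancer therapy starts. Section 5.9 allows termination for the incidence or severity of adverse reactions, and section 10.6.2 provides an independent, advisory DSMB. All of this stands and lowers the practical risk. What it does not do is make the death count: none of these provisions has a numerical threshold, and the weekly calls apply the same DLT definition.

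Two stronger readings are tempting, and the documents do not support them.

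- *A permanent stop also escapes the rule.* A reader might infer that surgery cancelled, or radiation abandoned, is not a delay. But the thresholds are elapsed days, and nothing in section 5.2.2.3.1 requires treatment to resume. Radiation stopped for an attributed event is past 3 days on day 4, and surgery is past 7 days on day 8. An ordinary reading already counts both; only a clarification is needed.
- *Skipped cisplatin doses escape the rule.* Sections 5.2.3 and 5.2.2.4.2 say "Any skipped doses will not be made up at the completion of radiation therapy" and "these doses will NOT be made up at end of treatment", so one might argue that a single skip, with the next dose 7 days later, is never more than 7 days. The one-day tolerance in sections 5.2.2.2.1 and 5.2.3 and the flow chart can make it 8 days, and a dose never given can be read as delayed without limit. The text does not settle this, and how many omitted doses matter is a clinical decision.

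**Conclusion.** The concern holds for attributed deaths and should be fixed. As written, a death attributed to pembrolizumab from an event arising after the patient's own CRT cannot count towards the more-than-2-of-8 rule, although the arm's lead-in analysis is still open and pembrolizumab is still being given. The conclusion rests on the wording of sections 5.2.2.3 and 5.2.2.3.1 and on the dosing schedule in the text, not on any assumed rate.

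A reader might go further and infer that the trial is likely to miss a needed stop, or has missed one. The documents do not support that. They give neither a DLT rate nor a rate of attributed death, so no missed-stop probability can be calculated. The document is Amendment 17 of 18 March 2021, and it does not say whether the lead-in is still open.

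**What to change.** Keep the delay criterion in section 5.2.2.3.1 and add: *any death attributed to pembrolizumab, from the first dose until the arm's lead-in analysis closes under section 5.2.2.3, is a DLT.* The end of the period should be the arm's closing date. A limit of four weeks after each patient's own CRT would still leave out later deaths among the first seven patients.

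Add two clarifications:

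- Attributed cancellation of surgery, or permanent discontinuation of radiation, counts as exceeding the delay threshold.
- A lead-in patient with a DLT stays in the tally even if replaced under section 5.8.

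Leave two matters to the sponsor's clinical judgement. The first is cisplatin omissions. A blanket rule on permanent discontinuation would make omission of dose 6 alone a DLT, although five doses give 5 × 40 = 200 mg/m², the cumulative dose cited in section 4.2.2.2. The second is the closing sentence of section 5.2.2.3 on events before surgery, where no arm has yet been assigned; rewording it could let a single event end the presurgical dose for everyone.

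The cost is protocol wording; section 7.2.3.1 already collects the deaths. The rule would trigger somewhat more often: 0.038 to 0.049 in the 10% plus 1 point example, and by about 0.4 to 12 percentage points over the whole assumed range. If the lead-in has already closed, the change affects only how its tally is reported, and the report should say that the definition was extended afterwards.

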#### **5.2.2.4 Dose Modification**

##### **5.2.2.4.1 Pembrolizumab - Dose Modification and toxicity management for immune-related AEs associated with pembrolizumab and combination therapy**

Adverse events (both non-serious and serious) associated with Pembrolizumab exposure may represent an immunologic etiology. These adverse events may occur shortly after the first dose or several months after the last dose of treatment. Pembrolizumab must be withheld for drug-related toxicities and severe or life-threatening AEs as per Table 3 below. See Section 5.6.1 and the most current investigator's brochure for supportive care guidelines, including use of corticosteroids.

Table 3

Dose Modification Guidelines for Drug-Related Adverse Events

General instructions:				
Immune-related AEs	Toxicity grade or conditions (CTCAE v 4.0)	Action taken to Pembrolizumab	Immune Related AE management with corticosteroid and/or other therapies	Monitor and follow-up
Pneumonitis	Grade 2	Withhold	
 
Administer corticosteroids (initial dose of 1-2 mg/kg prednisone or equivalent) followed by taper
 
Add prophylactic antibiotics for opportunistic infections
 
	
 
Monitor participants for signs and symptoms of pneumonitis
 
Evaluate participants with suspected pneumonitis with radiographic imaging and initiate corticosteroid treatment
 

	Grade 3 or 4, or recurrent Grade 2	Permanently discontinue		•
Diarrhea / Colitis	Grade 2 or 3	Withhold	
 
• Administer corticosteroids (initial dose of 1-2 mg/kg prednisone or equivalent) followed by taper
 
	
 
• Monitor participants for signs and symptoms of enterocolitis (ie, diarrhea, abdominal pain, blood or mucus in stool with or without fever) and of bowel perforation (ie, peritoneal signs and ileus). Participants with <math>\geq</math> Grade 2 diarrhea suspecting colitis should consider GI consultation and performing endoscopy to rule out colitis.
 
• Participants with diarrhea/colitis should be advised
 

	Grade 4	Permanently discontinue		to drink liberal quantities of clear fluids. If sufficient oral fluid intake is not feasible, fluid and electrolytes should be substituted via IV infusion.
--	---------	-------------------------	--	---

AST / ALT elevation or Increased bilirubin AST / ALT elevation or Increased bilirubin	Grade 2	Withhold	
 
Administer corticosteroids (initial dose of 0.5- 1 mg/kg prednisone or equivalent) followed by taper
 
	
 
Monitor with liver function tests (consider weekly or more frequently until liver enzyme value returned to baseline or is stable)
 

	Grade 3 or 4	Permanently discontinue	
 
Administer corticosteroids (initial dose of 1-2 mg/kg prednisone or equivalent) followed by taper
 
	
 
Monitor with liver function tests (consider weekly or more frequently until liver enzyme value returned to baseline or is stable)
 

Type 1 diabetes mellitus (T1DM) or Hyperglycemia	Newly onset T1DM or Grade 3 or 4 hyperglycemia associated with evidence of $\beta$ -cell failure	Withhold	
 
Initiate insulin replacement therapy for participants with T1DM
 
Administer anti-hyperglycemic in
 
	
 
Monitor participants for hyperglycemia or other signs and symptoms of diabetes.
 

			participants with hyperglycemia	
Hypophysitis	Grade 2	Withhold	
 
Administer corticosteroids and initiate hormonal replacements as clinically indicated.
 
	
 
Monitor for signs and symptoms of hypophysitis (including hypopituitarism and adrenal insufficiency)
 

	Grade 3 or 4	Withhold or permanently discontinue 		
Hyperthyroidism	Grade 2	Continue	
 
Treat with non-selective beta-blockers (eg, propranolol) or thionamides as appropriate
 
	
 
Monitor for signs and symptoms of thyroid disorders.
 

	Grade 3 or 4	Withhold or permanently discontinue 		
Hypothyroidism	Grade 2-4	Continue	
 
Initiate thyroid replacement hormones (eg, levothyroxine or liothyroinine) per standard of care
 
	
 
Monitor for signs and symptoms of thyroid disorders.
 

Nephritis grading according to increased creatinine or acute kidney injury	Grade 2	Withhold	
 
Administer corticosteroids (prednisone 1-2 mg/kg or equivalent) followed by taper.
 
	
 
Monitor changes of renal function
 

	Grade 3 or 4	Permanently discontinue		
Neurological Toxicities	Grade 3 or 4	Permanently discontinue	
 
Based on severity of AE administer corticosteroids
 
	
 
Ensure adequate evaluation to confirm etiology and/or exclude other causes
 

Myocarditis	Grade 1	Withhold	
 
Based on severity of AE administer
 
	
 
Ensure adequate evaluation to
 

	Grade 2, 3 or 4	Permanently discontinue	corticosteroids	confirm etiology and/or exclude other causes
--	-----------------	-------------------------	-----------------	--

All other immune-related AEs	Intolerable/persistent Grade 2	Withhold	
 
Based on type and severity of AE administer corticosteroids
 
	
 
Ensure adequate evaluation to confirm etiology and/or exclude other causes
 

	Grade 3	Withhold or discontinue based on the type of event. Events that require discontinuation include and not limited to: Gullain-Barre Syndrome, encephalitis		
	Grade 4 or recurrent Grade 3	Permanently discontinue		

1. Withhold or permanently discontinue Pembrolizumab is at the discretion of the investigator or treating physician.

**NOTE:**

For participants with Grade 3 or 4 immune-related endocrinopathy where withhold of Pembrolizumab is required, Pembrolizumab may be resumed when AE resolves to ≤ Grade 2 and is controlled with hormonal replacement therapy or achieved metabolic control (in case of T1DM).

Dosing interruptions are permitted in the case of medical / surgical events or logistical reasons not related to study therapy (e.g., elective surgery, unrelated medical events, patient vacation, and/or holidays). Subjects should be placed back on study therapy within 3 weeks of the scheduled interruption, unless otherwise discussed with the Sponsor. The reason for interruption should be documented in the patient's study record. If a pembro dosed is held, then that dose is considered missed.

